### 5.7.2 Carboplatin/Etoposide Dose Reductions and Delays

If a subject experiences an adverse event attributable to carboplatin or etoposide, carboplatin or etoposide may either be interrupted or the dose reduced.

If a dose reduction or delay is required for carboplatin and/or etoposide, the Investigator should follow procedures as defined in the locally approved product label or applicable Summary of Product Characteristics (SmPC). Section [5.7.2.1](#) outlines suggested dose

reductions for carboplatin/etoposide if above information is not available. PD and/or PK samples will not be drawn during carboplatin and/or etoposide dose delays.

### **5.7.2.1 Guidelines for Carboplatin and Etoposide Dose Reductions and Delays**

The below guidelines are suggested, unless described as mandatory. If a dose reduction or delay is required for carboplatin and/or etoposide, the Investigator should follow procedures according to institutional guidelines, the locally approved product label, local practice, or applicable SmPC. If the Investigator considers an event attributable to carboplatin and/or etoposide, the Investigator may consider reducing carboplatin and/or etoposide, but not veliparib/placebo. Suggested guidelines for dose reduction, delay, and discontinuation are included in [Table 16](#) and [Table 19](#) (if locally approved product label, local standard of care guideline or applicable SmPC for carboplatin/etoposide combination chemotherapy are not available).

All carboplatin and/or etoposide dose reductions are permanent. Re-escalation of the dose of therapy is not allowed. All toxicities should have resolved to grade 1 or less prior to initiation of a new cycle of therapy, with the exception of anemia, alopecia, neuropathy, and non-treatment related clinically insignificant laboratory abnormalities.

If toxicity precludes the initiation of the dosing of carboplatin/etoposide in the cycle, and veliparib doses on Days -2 and -1 of the cycle have already been administered, veliparib should be administered again once the toxicity resolves for 2 days prior to carboplatin/etoposide dosing. In such a case, a new supply of veliparib/placebo is to be dispensed, and Day -2 and Day -1 are to be repeated for that cycle.

For Phase 1 ONLY: PD and/or PK samples will not be drawn during carboplatin and/or etoposide dose delays. If the Investigator considers an event attributable to carboplatin and/or etoposide and not veliparib, the Investigator may consider reducing the dose of both agents.

### 5.7.2.1.1 Hematologic Toxicity

If chemotherapy must be withheld due to hematologic toxicity, CBC and platelet counts should be obtained weekly via central labs (if done locally, sample MUST be split for central lab) until the counts reach the lower limits for treatment as outlined. The treatment schedule will then proceed in the usual sequence.

#### **Neutropenia or Febrile Neutropenia**

For febrile neutropenia with absolute neutrophil count (ANC)  $< 500/\text{mm}^3$  and a single temperature of  $> 38.3^\circ\text{C}$  ( $101^\circ\text{F}$ ) or a sustained temperature of  $\geq 38^\circ\text{C}$  ( $100.4^\circ\text{F}$ ) for more than one hour, requiring intravenous antibiotics:

- a. Doses of both carboplatin and etoposide drugs should be reduced to the next lower dose level for all subsequent cycles of chemotherapy. Suggested dose reduction levels are outlined in [Table 14](#).
- b. Implement dose reductions, as outlined in [Table 19](#).
- c. Initiate prophylactic neutrophil growth factors (e.g., G-CSF) after the first episode and in accordance with local SOC practices, ASCO or NCCN guidelines.
- d. If ANC counts do not recover within 3 weeks, discontinue all protocol therapy.

For treatment delays of more than 7 days due to neutropenia, carboplatin and etoposide should be dose-reduced to next lower dose level for all subsequent cycles of chemotherapy, as outlined in [Table 19](#).

For nadir neutropenia in the absence of fever or with fever that is successfully treated by oral antibiotics, there will be no dose adjustment.

ANC must be  $\geq 1,500/\text{mm}^3$  on Day 1 of each cycle (mandatory). If the ANC is lower than  $1,500/\text{mm}^3$ , then dosing of all drugs (carboplatin, etoposide and veliparib) will be delayed until recovery to the required ANC.

### **Platelets**

For Grade 4 nadir platelet count decrease (thrombocytopenia) (platelets < 25,000 mm^3), the dose of both carboplatin and etoposide should be reduced to next lower dose level from the previous dose for all subsequent cycles of chemotherapy. Implement dose reductions 1 and 2 for the first and second episodes, respectively as outlined in [Table 19](#). If counts do not recover within 3 weeks, discontinue all protocol therapy.

Platelet count must be > 100,000/mm^3 on Day 1 of each cycle (mandatory). Doses of all drugs (carboplatin, etoposide and veliparib) should be delayed until platelet count recovers to > 100,000/mm^3.

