**Table 16. Guidelines for Veliparib, Carboplatin, and Etoposide Dose Reduction Levels During Combination Therapy**

Dose Reductions	Carboplatin	Etoposide a	Veliparib b
Starting Dose	AUC 5	100 mg/m 	Phase 1: As assigned Phase 2: 240 mg BID
Dose Reduction 1	AUC 4	75 mg/m 	Phase 1: Next lower DL (assigned –1) Phase 2: 200 mg BID
Dose Reduction 2	No Additional Reductions Allowed	55 mg/m 	Phase 1: Next lower DL (assigned –2) Phase 2: 160 BID

a. Refer to Section 5.7.2.1.2 for etoposide dose reduction guidelines related to bilirubin.

b. Refer to Section 5.7.1 for veliparib dose reduction guidelines for maintenance therapy. "Next lower DL" refers to the daily dose levels tested in the dose escalation part of the study. The dose of each drug can be reduced independently based on the observed toxicities. For veliparib dose level of 80 mg (Phase 1 only), Dose Reduction 1 is to 60 mg, Dose Reduction 2 is to 40 mg.

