### **Anemia**

No dose reductions will be made for anemia. Subjects should be supported per the treating physician's discretion. The use of RBC transfusions for anemia will be allowed as clinically indicated and as per local standard of care or current NCCN guidelines. The use of growth factors for anemia is not permitted during Phase 1 Cycle 1.

If more than two dose modifications of carboplatin and etoposide are required for hematologic toxicity, e.g., in cases where an additional dose modification is needed for a toxicity which was not observed earlier, please consult the AbbVie TA MD.

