**Table 19. Suggested Guidelines for Carboplatin/Etoposide Dose Delay or Reduction**

Adverse Event	Carboplatin Dose	Etoposide Dose
ANC < 1,500/mm  Day 1 of Cycle	Hold next cycle until ANC ≥ 1,500/mm  .	Hold next cycle until ANC ≥ 1,500/mm  .
Treatment delays of > 7 days due to neutropenia	Implement Dose Reduction 1 for 1 st episode.	Implement Dose Reduction 1 for 1 st episode and Dose Reduction 2 for 2 nd episode.
Grade 3/4 febrile neutropenia with ANC < 500/mm  , requiring IV antibiotics	Implement Dose Reduction 1 for 1 st episode. Initiate Prophylactic G-CSF after 1 st episode.	Implement Dose Reduction 1 for 1 st episode and Dose Reduction 2 for 2 nd episode. Initiate Prophylactic G-CSF after 1 st episode.
Grade 3 nausea, vomiting or Grade 4 vomiting	Hold next cycle until resolution to Grade 1 or better. If more than 2 weeks dose delay is required consult with AbbVie TA MD.	Hold next cycle until resolution to Grade 1 or better. If more than 2 weeks dose delay is required consult with AbbVie TA MD.
Platelets < 100,000/mm  Day 1 of Cycle	Hold next cycle until platelets ≥ 100,000/mm  .	Hold next cycle until platelets ≥ 100,000/mm  .
Grade 4 thrombocytopenia	Implement Dose Reduction 1 for 1 st episode.	Implement Dose Reduction 1 for 1 st episode and Dose Reduction 2 for 2 nd episode.
Bilirubin > 1.5 – 3.0 × ULN	No Change	Reduce dose to 50 mg/m 
Bilirubin > 3 – 5 × ULN	No Change	Reduce dose to 30 mg/m 
Bilirubin > 5 × ULN	Hold if bilirubin does not improve to ≤ 5 × ULN within 3 weeks of first occurrence, discontinue protocol therapy	Hold if bilirubin does not improve to ≤ 5 × ULN within 3 weeks of first occurrence, discontinue protocol therapy
Any other Grade 3/4 toxicity	Per local SmPC/institution guidelines	Per local SmPC/institution guidelines

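### The Grade 4 thrombocytopenia text steps carboplatin down at a second episode, but Table 16 bars a second carboplatin reduction and Table 19 has no entry for one

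*Protocol*

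**What the plan says.** The Platelets paragraph of Protocol Section 5.7.2.1.1 covers a Grade 4 platelet nadir in two sentences. The first says "the dose of both carboplatin and etoposide should be reduced to next lower dose level from the previous dose for all subsequent cycles". The second says "Implement dose reductions 1 and 2 for the first and second episodes, respectively as outlined in" Table 19. Neither sentence treats carboplatin differently from etoposide.

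Table 16 sets the dose levels. Etoposide has two reductions, from 100 to 75 to 55 mg/m². Carboplatin has one, from AUC 5 to AUC 4, and its Dose Reduction 2 cell reads "No Additional Reductions Allowed".

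Table 19 separates the drugs in its Grade 4 thrombocytopenia row. The carboplatin cell reads "Implement Dose Reduction 1 for 1 st episode" and stops there. The etoposide cell goes on: "episode and Dose Reduction 2 for 2" (that is, the second episode).

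In the same section, item a of the febrile-neutropenia text says "Suggested dose reduction levels are outlined in" Table 14. Table 14 (Section 5.5.2.1) gives dosage form and route for the two commercial drugs and contains no reduction levels.

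**The concern.** A dose-modification rule should give the same answer whether a site reads the paragraph or the table it cites. Here the paragraph, taken on its own words, asks for two carboplatin steps, while the level table permits one and the event table lists one. A site facing a second Grade 4 nadir could look for a level that is not defined, leave carboplatin unchanged, stop it, or call the sponsor, and the protocol's own guidance does not settle which.

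Subject safety is the main stake, because this is the point at which marrow toxicity has recurred. There is a smaller reporting consequence. SAP Section 9.0 summarizes carboplatin dose intensity and the number of subjects with a reduction of each drug, and those descriptive tables would mix different handling of the same event.

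**Working it through.** No power, event count or alpha enters this point, so the check is a side-by-side reading of the current text. The number of permitted steps is counted for each drug after Grade 4 thrombocytopenia.

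| Source | Carboplatin, 1st episode | Carboplatin, 2nd episode | Etoposide, 1st episode | Etoposide, 2nd episode |
|---|---|---|---|---|
| 5.7.2.1.1, Platelets text | Reduction 1 | Reduction 2 | Reduction 1 | Reduction 2 |
| Table 16 | AUC 5 to AUC 4 | Further reduction expressly barred | 100 to 75 mg/m² | 75 to 55 mg/m² |
| Table 19, Grade 4 thrombocytopenia row | Reduction 1 | No entry | Reduction 1 | Reduction 2 |

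**Step 1: etoposide.** All three sources give 2 steps, so they agree for first and second episodes.

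**Step 2: carboplatin.** The text gives 2 steps, Table 16 gives 1, and Table 19 gives 1. The difference of 2 − 1 = 1 step falls at the second episode. The two tables are not equally strong. Table 16 forbids the step; Table 19 is only silent about it.

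**Step 3: is a lower carboplatin level defined elsewhere?** Section 5.5.1.2 and Appendix E give maximum doses for AUC 5 (750 mg) and AUC 4 (600 mg) only. No level below AUC 4 appears.

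**Step 4: a second route to the same gap.** Table 19 also assigns carboplatin Reduction 1 for febrile neutropenia and for neutropenic delays of more than 7 days. Section 5.7.2.1 makes reductions permanent. Take a subject at AUC 4 for either reason who then has a *first* Grade 4 platelet nadir. The first Platelets sentence asks for a step below the previous dose, which Table 16 does not permit. Table 19 asks for Reduction 1, which is already in force. The instructions diverge at a first platelet episode as well.

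**Step 5: does other text fill the gap?** Section 5.4.1.1 says reductions may lead to one agent being discontinued while the other continues, but it does not say that a second Grade 4 nadir is the trigger. The consultation sentence under Anemia begins "If more than two dose modifications of carboplatin and etoposide are required for hematologic toxicity", so it starts only beyond two modifications and does not clearly cover a second episode.

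**Step 6: the cross-reference.** Item a of the febrile-neutropenia text points to Table 14 for the levels; the levels are in Table 16. Section 5.7.2.1 names Tables 16 and 19 correctly, so a careful reader can recover, but the pointer is wrong.

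**The case against.** The strongest reply is that the Platelets sentence ends by deferring to Table 19, and Table 19 treats the drugs separately. Read through that pointer, reductions 1 and 2 belong to etoposide and only reduction 1 to carboplatin, which agrees with Table 16. Nor does any rival dose exist, since nothing below AUC 4 is defined. This softens the conflict but does not remove it. The preceding sentence names both drugs and steps down from the previous dose, and a reader who follows the pointer finds an empty space for carboplatin at the second episode.

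The second reply is about reach. Sections 5.7.2 and 5.7.2.1 describe the guidance as suggested unless marked mandatory, and use it only where local label, SmPC or standard-of-care guidance is not available. The platelet reduction sentence is not marked mandatory. Both drugs are marketed products, so relatively few sites may need the fallback, and handling may differ between sites by design even after rewording. This stands, and it limits the size of the point.

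Two stronger readings are tempting, and the documents do not support either.

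- A reader might infer from the Anemia paragraph that two carboplatin modifications are permitted. That sentence is a trigger for consulting the sponsor and counts modifications of the two drugs together. It is compatible with one carboplatin step and two etoposide steps, and it grants no second carboplatin reduction.
- A reader might infer that repeat episodes will be more common in Arms A and B and so make carboplatin exposure differ by arm. Sections 3.3.3 and 3.7 do expect overlapping myelosuppression, but no document gives a rate of second episodes. In the randomized carboplatin/paclitaxel study in Section 3.3.3, no adverse event other than leukopenia and neutropenia rose by more than 5%, and reduction or discontinuation of backbone therapy was within ±3%. Section 3.7 adds that carboplatin delivery was not compromised. That study used 120 mg BID for 7 days with a different partner drug, against 240 mg BID on a 14-day schedule here, so it does not settle the matter. It does leave the inference without support.

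**Conclusion.** The point holds in a narrow form. For Grade 4 thrombocytopenia the Platelets text and Table 16 contradict each other on carboplatin at the second episode, and Table 19, which the text cites, leaves that case blank. The same gap is reached at a first episode in a subject already reduced for neutropenia. The Table 14 reference is a separate and plain error.

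This is an internal inconsistency in operative text, not a flaw in the design. It concerns only subjects with those events at sites that rely on the protocol's fallback guidance; their number cannot be estimated from the documents. It does not touch the primary analysis, alpha, power or sample size. Its priority is low, but it bears on subject safety and is cheap to correct. The conclusion assumes that the paragraph and tables are meant to be read together and that no separate site instruction already resolves the case.

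**What to change.** Reconcile the Platelets paragraph of Section 5.7.2.1.1 with Tables 16 and 19 so that one carboplatin instruction applies after a second Grade 4 episode, and after a first episode in a subject whose carboplatin was already reduced for neutropenia. State it for each drug separately, and fill the blank in the Table 19 carboplatin cell to match. Which instruction is right is for the sponsor's clinical team; this review does not propose one.

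In item a of the febrile-neutropenia text, replace the reference to Table 14 with a reference to Table 16.

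The cost is protocol wording only. No analysis, data collection or sample-size change follows.

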### **Anemia**

No dose reductions will be made for anemia. Subjects should be supported per the treating physician's discretion. The use of RBC transfusions for anemia will be allowed as clinically indicated and as per local standard of care or current NCCN guidelines. The use of growth factors for anemia is not permitted during Phase 1 Cycle 1.

If more than two dose modifications of carboplatin and etoposide are required for hematologic toxicity, e.g., in cases where an additional dose modification is needed for a toxicity which was not observed earlier, please consult the AbbVie TA MD.

#### **5.7.2.1.2 Non-Hematological Toxicity**

##### **Gastrointestinal Toxicity: Nausea and Vomiting**

All subjects should receive antiemetics\* to prevent nausea and vomiting. Specific antiemetic therapy is left to the discretion of the treating physician (steroids and 5-HT3 antagonists should be used). For vomiting Grade ≥ 3, consider hospital admission and/or use of aprepitant, if possible. Nausea/vomiting should have resolved to Grade 1 or less prior to initiation of next treatment cycle. Do not modify carboplatin and/or etoposide doses due to nausea/vomiting.

- \* Aprepitant, when given once daily for 14 days as a 100 mg capsule with an oral contraceptive containing 35 mcg of ethinyl estradiol and 1 mg of norethindrone, decreased the AUC of ethinyl estradiol by 43% and decreased the AUC of norethindrone by 8%. Women of childbearing potential using pregnancy contraception that includes ethinyl estradiol should not receive Aprepitant for the treatment of nausea/delayed emesis. Subjects may change to a different method of contraception if they wish to use Aprepitant.

### **Hepatic Toxicity**

For bilirubin  $> 1.5 - 3.0 \times \text{ULN}$ , not attributable to underlying disease, reduce the dose of etoposide to  $50 \text{ mg/m}^2$ . For bilirubin  $> 3 - 5 \times \text{ULN}$  reduce the dose of etoposide to  $30 \text{ mg/m}^2$ . For bilirubin  $> 5 \times \text{ULN}$  hold etoposide or hold all treatment if starting the next treatment cycle. When bilirubin resolves to  $\leq 5 \times \text{ULN}$ , treatment can be resumed, with etoposide dose to  $30 \text{ mg/m}^2$ . If bilirubin does not improve to  $\leq 5 \times \text{ULN}$  within 3 weeks of first occurrence, discontinue protocol therapy.

#### **5.7.2.1.3 Other Grade 3/4 Non-Hematologic Toxicity**

Other non-hematologic Grade 3/4 toxicity should be managed as per local SmPC guidelines and institutional standard practices.

**Table 19. Suggested Guidelines for Carboplatin/Etoposide Dose Delay or Reduction**

Adverse Event	Carboplatin Dose	Etoposide Dose
ANC < 1,500/mm  Day 1 of Cycle	Hold next cycle until ANC ≥ 1,500/mm  .	Hold next cycle until ANC ≥ 1,500/mm  .
Treatment delays of > 7 days due to neutropenia	Implement Dose Reduction 1 for 1 st episode.	Implement Dose Reduction 1 for 1 st episode and Dose Reduction 2 for 2 nd episode.
Grade 3/4 febrile neutropenia with ANC < 500/mm  , requiring IV antibiotics	Implement Dose Reduction 1 for 1 st episode. Initiate Prophylactic G-CSF after 1 st episode.	Implement Dose Reduction 1 for 1 st episode and Dose Reduction 2 for 2 nd episode. Initiate Prophylactic G-CSF after 1 st episode.
Grade 3 nausea, vomiting or Grade 4 vomiting	Hold next cycle until resolution to Grade 1 or better. If more than 2 weeks dose delay is required consult with AbbVie TA MD.	Hold next cycle until resolution to Grade 1 or better. If more than 2 weeks dose delay is required consult with AbbVie TA MD.
Platelets < 100,000/mm  Day 1 of Cycle	Hold next cycle until platelets ≥ 100,000/mm  .	Hold next cycle until platelets ≥ 100,000/mm  .
Grade 4 thrombocytopenia	Implement Dose Reduction 1 for 1 st episode.	Implement Dose Reduction 1 for 1 st episode and Dose Reduction 2 for 2 nd episode.
Bilirubin > 1.5 – 3.0 × ULN	No Change	Reduce dose to 50 mg/m 
Bilirubin > 3 – 5 × ULN	No Change	Reduce dose to 30 mg/m 
Bilirubin > 5 × ULN	Hold if bilirubin does not improve to ≤ 5 × ULN within 3 weeks of first occurrence, discontinue protocol therapy	Hold if bilirubin does not improve to ≤ 5 × ULN within 3 weeks of first occurrence, discontinue protocol therapy
Any other Grade 3/4 toxicity	Per local SmPC/institution guidelines	Per local SmPC/institution guidelines

## 6.0 Adverse Events

The investigator will monitor each subject for clinical and laboratory evidence of adverse events on a routine basis throughout the study. The investigator will assess and record any adverse event in detail including the date of onset, event diagnosis (if known) or sign/symptom, severity, time course (end date, ongoing, intermittent), relationship of the adverse event to study drug, and any action(s) taken. For serious adverse events considered as having "no reasonable possibility" of being associated with study drug, the investigator will provide another cause of the event. For adverse events to be considered

intermittent, the events must be of similar nature and severity. Adverse events, whether in response to a query, observed by site personnel, or reported spontaneously by the subject will be recorded.

All adverse events will be followed to a satisfactory conclusion.

## **6.1 Definitions**

### **6.1.1 Adverse Event**

An adverse event (AE) is defined as any untoward medical occurrence in a patient or clinical investigation subject administered a pharmaceutical product and which does not necessarily have a causal relationship with this treatment. An adverse event can therefore be any unfavorable and unintended sign (including an abnormal laboratory finding), symptom, or disease temporally associated with the use of a medicinal (investigational) product, whether or not the event is considered causally related to the use of the product.

Such an event can result from use of the drug as stipulated in the protocol or labeling, as well as from accidental or intentional overdose, drug abuse, or drug withdrawal. Any worsening of a pre-existing condition or illness is considered an adverse event.

Worsening in severity of a reported adverse event should be reported as a new adverse event. Laboratory abnormalities and changes in vital signs are considered to be adverse events only if they result in discontinuation from the study, necessitate therapeutic medical intervention, (meets protocol specific criteria [see Section 6.8 regarding toxicity management]) and/or if the investigator considers them to be adverse events.

An elective surgery/procedure scheduled to occur during a study will not be considered an adverse event if the surgery/procedure is being performed for a pre-existing condition and the surgery/procedure has been pre planned prior to study entry. However, if the pre-existing condition deteriorates unexpectedly during the study (e.g., surgery is performed earlier than planned), then the deterioration of the condition for which the elective surgery/procedure is being done will be considered an adverse event.

### **6.1.2 Deaths**

For this protocol, mortality is an efficacy endpoint. Deaths that occur during the protocol specified adverse event reporting period (Section 6.5) that are attributed by the investigator solely to progression of disease under study should be recorded only on the Study Completion/Early Discontinuation eCRF. All other on-study deaths, regardless of relationship to study drug, must be recorded on the Adverse Event eCRF and immediately reported to the Sponsor (Section 6.1.4).

Death should be considered an outcome and not a distinct event. The event or condition that caused or contributed to the fatal outcome should be recorded as the single medical concept on the Adverse Event eCRF. Generally, only one such event should be reported. The term "sudden death" should only be used for the occurrence of an abrupt and unexpected death due to presumed cardiac causes in a patient with or without preexisting heart disease, within 1 hour of the onset of acute symptoms or, in the case of an unwitnessed death, within 24 hours after the patient was last seen alive and stable. If the cause of death is unknown and cannot be ascertained at the time of reporting, "unexplained death" should be recorded on the Adverse Event eCRF. If the cause of death later becomes available (e.g., after autopsy), "unexplained death" should be replaced by the established cause of death.

During survival follow-up, deaths should be recorded on Survival eCRF.

